### **3.0 Objectives/Aims**

The specific aims are to determine:

**Aim 1:** Feasibility and acceptability of sleep extension intervention. Rationale: Analysis of recruitment, retention and participant program evaluation will provide feasibility and acceptability data. Hypothesis: Sleep extension intervention will be feasible and acceptable to the target population. Approach: Feasibility will be determined through analysis of recruitment and retention. Acceptability will be determined through participant evaluation.

**Aim 2:** Efficacy of sleep extension intervention on primary outcomes of glucose metabolism. Rationale: Short sleep duration was associated with abnormal glucose metabolism in women with previous GDM. Sleep optimization in short sleeping individuals without diabetes resulted in improved insulin resistance. Hypothesis: Sleep extension intervention will result in improved glycemic control. Approach: A randomized controlled trial of an 8-week sleep extension intervention compared to a healthy living information control group on glucose metabolism as measured by an oral glucose tolerance test and A1C at baseline and at the end of intervention.

**Aim 3:** Efficacy of sleep extension intervention on secondary outcomes of weight, appetite regulating hormones, energy expenditure, inflammatory markers, depressive symptoms and subjective sleep quality.

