### **Study protocol**

#### **1. Baseline assessment:**

- One week of actigraphy will be recorded using an actiwatch spectrum. If during this assessment it is found that their sleep duration is  $\geq 7$  hours during the weekdays or work days, they will not be able to participate further.
- Subjects will answer sleep, physical activity, depression questionnaires, quality of life, anxiety symptoms and perceived stress symptoms.
- Weight, height, waist and hip circumference, and neck circumference will be obtained
- Eating behaviors, appetite and 24 hour food recall will be obtained through questionnaires.
- 
- At the end of one week, they will return to have a 75-gram oral glucose tolerance test (OGTT) done at the clinical research center (see below procedure).

- Blood will be assayed for A1C, serum creatinine, lipid panel and CBC.
- Blood will be saved for assay for genetic analysis, appetite regulating hormones (leptin, ghrelin, PYY, 2-arachidonoylglycerol (2-AG)), and inflammatory markers (CRP, IL-1, IL-6), and metabolomics profiles.
- Stool sample will be collected for stool microbiome assay
- Resting metabolic rate will be performed
- Additional serum samples will be stored for future analysis

2. The subjects will then be randomized to healthy living control group or sleep extension group for 6 weeks (see blow detail).
3. At week 6, they will be given an actiwatch to wear for one week. At week 7, the following procedures will take place
  - They will return to the CRC to have a repeated 75-gram OGTT done.
  - Weight will be obtained
  - Subjects will answer sleep, depression questionnaires, quality of life, anxiety symptoms and perceived stress symptoms.
  - Eating behaviors, appetite and 24 hour food recall will be obtained through questionnaires.
  - Blood will be assayed for A1C, lipid panel.
  - Blood will be saved for later assay for appetite regulating hormones (leptin, ghrelin, PYY, 2-arachidonoylglycerol (2-AG)), and inflammatory markers (CRP, IL-1, IL-6) and metabolomics profiles.
  - Stool sample will be collected for stool microbiome assay
  - Resting metabolic rate will be performed
  - Additional serum samples will be stored for future analysis
  - Participant evaluation of the program will be obtained through questionnaires and interview.
4. At week 10, subject will be given an actiwatch for one week. And,
  - They will return to the CRC to have fasting glucose and insulin level done.
  - Weight will be obtained

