**3. Oral Glucose Tolerance Test (OGTT).** After an overnight fast, the subject will arrive at the CRC between 8-9 am. Blood samples will be obtained at 0 minutes for glucose and insulin. Then 75 grams glucose solution will be given orally. Blood samples will be obtained at 30, 60, 90, 120 minutes for glucose and insulin. Extra blood samples will also be obtained at 0 minutes and stored for further analysis. **Total blood volume 60 ml per one OGTT visit.**

**4. Blood samples** will be obtained for lipid panel, creatinine and A1C at baseline and at week 6. CBC will be obtained at baseline. Fasting glucose and insulin will be obtained at week 10. Blood will be saved for later assay for genetic analysis, appetite regulating hormones (leptin, ghrelin, PYY, 2-arachidonoylglycerol (2-AG)), and inflammatory markers (CRP, IL-1, IL-6) and metabolomics profiles. **Total blood sample 20 ml at each visit.**

**5. Microbiome** Stool samples to measure the gut microbiome will be collected at week 0 and week 6. Changes in sleep may alter the gut microbiome and potentially influence glycemia. Participants will be provided a collection device (Easysampler®, ALPCO, Inc.) and return the specimen at a subsequent visit. Remaining stool samples will be stored in a freezer at the College of Medicine for later analysis by UIC researchers.

**6. Resting energy expenditure:** Oxygen consumption will be measured through indirect calorimetry using the Vyntus CPX system metabolic cart (Vyaire Medical, Mettawa, IL). In this test, a canopy hood is placed over the subject's head as he/she reclines in bed. One end of the canopy has tubing connected to the metabolic cart, while the other end of the canopy is open to room air. During the 30-40 minute procedure, expired gases are measured and resting energy expenditure is calculated using the Harris-Benedict equations. This will be performed during fasting.

**7. Feasibility and acceptability of Sleep extension:** Feasibility will be determined through analysis of recruitment (number recruited, screened, eligible, and consented) and retention (% session participation, program completion rates). Acceptability will be determined through participant evaluation (written evaluation and interview at program completion). See Appendix B.

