### **Protocol Overview**

	Urine preg test Screening questionnaire	A1C	OGTT, and blood samples	Questionnaires, actigraphy (1 week)	Stool sample	Energy expenditure	Acceptability assessment
Screening	X	X					
Week 0-1		X	X	X	x	x	
RANDOMIZATION							
Week 6-7		X	X	X	x	x	X
Week 10			Fasting glucose and insulin	X			

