### **Protections Against Risk**

Methods to minimize risk include:

1. Minimization of bleeding, irritation, discomfort, or infection at the blood draw site. The risk for these problems is very minor and is minimized by following standardized procedures. Blood draws will be done using sterile technique and standardized procedures. These will be performed by trained personnel.
2. Completing self-report measures on sleep and depressive mood may cause subjects some emotional distress. The risk is minimal. In our previous studies with the same population, no subjects reported emotional distress with these measures. However, study staff will be aware of the possibility and address any concerns that are voiced.
3. Actiwatch could cause minor irritation, however, this is rare. Should this happen, the subjects can choose to discontinue the study at anytime.
4. Drinking glucose solution may be unpleasant for some subjects. However, this solution is used in standard medical care to screen for diabetes. The subjects can discontinue their participation if deemed intolerable.
5. Should a subject require medical or other professional intervention due to an adverse event or illness, treatment may be obtained through the UIC Medical Center, the subject's regular doctor, or the treatment center or clinic of their choice. Subjects will be provided contact information for the PI should they want to talk to her about their illness or injury.
6. To prevent coercive contact from the application and coach, all email outreach is pre-scripted and user contact information is never revealed. Outreach emails will state that the coach has noticed they have not completed sleep diaries or worn the Fitbit in a few days and ask if they would like troubleshooting help or to return to the program. It will not include any coercive language or pressure. Email communication will be limited to pre-scripted content reminders and participant outreach.
7. Participants will be informed that they may discontinue the intervention at any time. In the event that an adverse event is experienced participants will be instructed to contact [name] or [name]. Phone numbers will be provided through which one of the investigators can be reached 7 days/week, 24 hours/day.

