### **Data Safety Monitoring Plan**

**CO PIs: [name], [name], [name]**

The risk associated with this study is minimal for the interventions and data collection methods employed by the study. The potential for a serious adverse event is very low. [name] will be the primary monitor, and a Safety Monitoring Committee will share the responsibility of monitoring the data.

The individuals responsible for data safety and monitoring will be [name], [name], [name] and [name], and a Study Monitoring Committee (SMC). A SMC will be appointed to provide oversight and monitoring of our data on an annual basis by individuals not directly associated with the study. The SMC will consist of: (1) [name] , PhD, RN, Assistant Professor, Department of Biobehavioral Health Science, College of Nursing; (2) [name], Professor of Medicine, Department of Medicine, Endocrinology, Diabetes and Metabolism; and (3) [name], RN, Assistant Professor, Department of Biobehavioral Health Science, College of Nursing; —all at UIC. Drs. [name], [name] and [name] have expertise in reviewing the scientific design, conduct of study, intervention fidelity, evaluation of safety and risks to subjects, interpretation of data, and making recommendations concerning continuation, modification, suspension, or termination of the study.

[name], [name], [name] and [name], will meet with the SMC annually and provide a written and verbal progress report. The report will include a summary of cumulative recruitment, randomization, cumulative retention and attrition rate, study group demographics, adverse events, and data completeness and quality. The SMC will provide oversight of the study, as well as consider factors external to the study that may impact the safety of the participants or the ethics of the study. A written report of the meeting will be compiled that summarizes the review of data and outcomes, as well as any recommendations with respect to modification of the protocol.

Subjects feeling uncomfortable with the procedures can choose to terminate their participation at anytime. Should this occur, the PI will record the events and share the information with the investigators.

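### Acceptability of sleep extension (Aim 1) is assessed only at program completion (week 7), with no evaluation provided for women who withdraw earlier; if they are less satisfied, the result will look too favourable

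*Combined protocol and SAP*

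**What the plan says.** Section 3.0 makes feasibility and acceptability the first aim, with the hypothesis that the target population will accept the intervention. On measurement it says: "Acceptability will be determined through participant evaluation".

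Three places in section 6.0 fix the timing, and they agree:

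- Study procedures, item 7: "Acceptability will be determined through participant evaluation (written evaluation and interview at program completion". The item then refers to Appendix B.
- Study protocol, item 3, among the week 7 procedures: "Participant evaluation of the program will be obtained through questionnaires and interview". It is not repeated under week 10.
- Protocol Overview table: the column "Acceptability assessment" is marked only in the Week 6-7 row.

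Loss of participants is handled elsewhere. Item 7 places "retention (% session participation, program completion rates" under feasibility. Section 7.0 (Protections Against Risk, item 7) says: "Participants will be informed that they may discontinue the intervention at any time". The Data Safety Monitoring Plan in section 11.0 says: "Subjects feeling uncomfortable with the procedures can choose to terminate their participation at anytime". It continues: "Should this occur, the PI will record the events and share the information with the investigators".

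**The concern.** Acceptability is an opinion, and under this schedule it is collected from women who reach week 7. The intervention asks for a wearable tracker, daily review of the sleep log, bedtime reminders, weekly lessons and weekly calls. A woman who finds these burdensome has a reason to leave before that visit, so whether her opinion is observed may depend on what it is.

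Acceptability of sleep extension is described within one arm, so no comparison with control absorbs the selection. What is at stake is how the acceptability half of Aim 1 reads across to the target population. The Aim 2 glucose comparison is not affected.

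**Working it through.** **Step 1: is there a figure to reproduce?** No. The documents give no expected dropout, no acceptability target and no binary definition of acceptable. The check is therefore of the text, followed by an illustration.

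**Step 2: who is asked under the schedule?**

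- Completes the program and attends week 7: asked.
- Stops the intervention but attends week 7: asked, because the visit list goes by week and not by adherence.
- Withdraws, or otherwise does not reach week 7: no evaluation is provided in the supplied text.

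The gap is the third group only.

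**Step 3: does another source give that group's opinion?**

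- Session participation and completion rates count who stayed. They do not separate leaving out of dislike from leaving for unrelated reasons.
- The investigator's record of terminations sits in the safety plan, concerns discomfort with procedures, and is not linked to Aim 1.
- Outreach to women who lapse (section 7.0, Protections Against Risk, item 6) offers troubleshooting or a return to the program and asks for no evaluation.

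**Step 4: possible size (illustration).**

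Inputs from the documents: 60 women randomized (section 2.0) at 2:1 (section 12.0), so 60 × 2/3 = 40 on sleep extension.

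Assumptions: a binary rating; a favourable proportion among completers of C = 90%; a fraction lost before week 7 of d = 10%, 20% or 30%; a favourable proportion among those lost of L = 0%, 30%, 60% or 90%.

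- Rate among all randomized = (1 − d) × C + d × L
- Overstatement by the completer rate = d × (C − L)

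| d | L = 0% | L = 30% | L = 60% | L = 90% |
|---|---|---|---|---|
| 10% | 9 points | 6 | 3 | 0 |
| 20% | 18 | 12 | 6 | 0 |
| 30% | 27 | 18 | 9 | 0 |

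Worst cell: 0.7 × 90% + 0.3 × 0% = 63% of all randomized, against 90% reported. The last column shows no overstatement when leavers think as completers do. If leavers were more favourable than completers, the sign would reverse.

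**Step 5: bounds without assuming leavers' views.** At 20% lost, 8 of 40 are not asked and 32 are. If 29 of the 32 are favourable (90.6%), the rate among all randomized lies between 29/40 = 72.5% and (29 + 8)/40 = 37/40 = 92.5%. Each woman not asked widens this range by 1/40 = 2.5 points.

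**The case against.** The best defence is that an end-of-program evaluation read beside retention is a reasonable choice for a pilot. The rationale for Aim 1 names recruitment, retention and program evaluation together as the source of feasibility and acceptability data, so a reader would see completion rates next to the ratings and could judge the loss. The weekly calls and the record of terminations are also channels for learning why women disengage. And Appendix B may hold instructions on who receives the form.

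Much of this stands. Losses will be visible, and the absence of an exit evaluation cannot be fully confirmed without the appendix. It does not close the gap. The Approach sentence of Aim 1 assigns retention to feasibility and participant evaluation to acceptability. A count of leavers says nothing of their reasons, and the stated timing is the same in all three places in section 6.0.

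Some stronger readings are tempting but not supported:

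- A reader might infer that every dissatisfied woman goes unasked. Those who stop the intervention but attend week 7 are scheduled for the evaluation.
- A reader might infer that upward bias is established. It is conditional on leavers being less satisfied, and the documents contain nothing that shows this.
- A reader might infer that the $200 for completing the protocol (section 11.0) worsens the selection. It could equally keep dissatisfied women in until they are evaluated.

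**Conclusion.** The point holds as a gap in data collection. As written, the plan provides no acceptability evaluation for women randomized to sleep extension who withdraw before week 7, and nothing else in the supplied text records their view for Aim 1. The result will be too favourable if they are less satisfied than completers. That is plausible, but it is an inference.

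The 0 to 27 points shown above rest wholly on assumed loss, assumed ratings and a binary item that the protocol does not define. They show what could happen and do not estimate it. It would go too far to say that Aim 1 cannot be assessed: the documents set no threshold or formal test for acceptability, and retention gives partial context. This is a cheap improvement worth making, because opinions not collected when women leave cannot be recovered in the analysis.

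**What to change.** In section 6.0 (Study procedures item 7, the week 7 list and the Protocol Overview table), provide that every woman randomized to sleep extension is offered the existing written evaluation and a brief interview, including her reason for stopping. Offer it at week 7 or when she stops the program or withdraws, whichever comes first, by telephone or remotely and on a voluntary basis. If email is used, align Protections Against Risk item 6, which limits email to pre-scripted reminders and outreach. Check Appendix B for consistency.

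Report the results with the number evaluated out of all women randomized to sleep extension, and show completers and early leavers separately. Add a bound that counts non-responders as unfavourable only if the form contains a binary acceptability item.

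The cost is amendment wording and one short contact per dropout. Some leavers will not respond, and the figure may be less favourable than one from completers alone.

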### **Specimen collection**

The following describes specimen collection, processing, storage and assays.

- Blood collected will be labeled with coded ID only (containing no identifying information). Blood will be immediately processed to obtain plasma and will be stored. EDTA-preserved blood will be stored for future genetic analysis. (see below)
- Urine sample will be obtained for pregnancy testing during screening.
- CBC, serum creatinine, glucose and lipids will be assayed by Quest Diagnostics, with only coded ID. HbA1c will be assayed either by Quest Diagnostics or point-of-care testing.

- Stool specimen will be labeled with coded ID only (containing no identifying information) and stored for microbiota assay (see below).
- Blood, and stool samples will be stored at -80°C in the lab of [name] ([name]). Serum insulin, appetite regulating hormones and inflammatory markers will be assayed using commercially available kits. Stool microbiota and serum metabolomics will be assayed at a later time using standard protocol and procedures of the collaborators. EDT containing blood will be saved for genetic analysis. Samples will be stored for future research or until 15 years has passed. Samples will then be destroyed according to institutional policy.

### **Protocol Overview**

	Urine preg test Screening questionnaire	A1C	OGTT, and blood samples	Questionnaires, actigraphy (1 week)	Stool sample	Energy expenditure	Acceptability assessment
Screening	X	X					
Week 0-1		X	X	X	x	x	
RANDOMIZATION							
Week 6-7		X	X	X	x	x	X
Week 10			Fasting glucose and insulin	X			

## **7.0 Expected Risks/Benefits**

### **Potential Risks**

The potential risks to subjects include:

1. Bleeding, irritation, discomfort, or infection at the finger prick site (for A1C) and blood draw. The risk for these problems is very minor and is minimized by following standardized procedures using trained study personnel.
2. Loss of confidentiality. Standard procedures will be used to avoid breaches in confidentiality. We expect this risk to be low.
3. Completing self-report measures on sleep and mood may cause subjects some emotional distress.
4. Actiwatch may cause minor irritation but this is a rare event.
5. Risks associated with the intervention may include irritation due to wearing the Fitbit devices. No other risks are currently identified.
6. The intervention intends to increase sleep duration but it may or may not be able to do so. Since sleep is linked to glucose, it is possible that the glucose levels could worsen if the intervention could not increase sleep. However, this is expected to be minimal, if at all. The precaution is taken as subjects with diabetes are not eligible to participate.

7. Privacy and confidentiality: Despite best efforts, medical record collection could be compromised leading to a loss of privacy regarding confidential health information. To minimize this risk, no patient identifying information will be recorded in any research documents that are created. Indirect identifiers will be used to link data obtained from different methods. The key will be stored separately from the data and will be destroyed after data collection has been completed.

### **Protections Against Risk**

Methods to minimize risk include:

1. Minimization of bleeding, irritation, discomfort, or infection at the blood draw site. The risk for these problems is very minor and is minimized by following standardized procedures. Blood draws will be done using sterile technique and standardized procedures. These will be performed by trained personnel.
2. Completing self-report measures on sleep and depressive mood may cause subjects some emotional distress. The risk is minimal. In our previous studies with the same population, no subjects reported emotional distress with these measures. However, study staff will be aware of the possibility and address any concerns that are voiced.
3. Actiwatch could cause minor irritation, however, this is rare. Should this happen, the subjects can choose to discontinue the study at anytime.
4. Drinking glucose solution may be unpleasant for some subjects. However, this solution is used in standard medical care to screen for diabetes. The subjects can discontinue their participation if deemed intolerable.
5. Should a subject require medical or other professional intervention due to an adverse event or illness, treatment may be obtained through the UIC Medical Center, the subject's regular doctor, or the treatment center or clinic of their choice. Subjects will be provided contact information for the PI should they want to talk to her about their illness or injury.
6. To prevent coercive contact from the application and coach, all email outreach is pre-scripted and user contact information is never revealed. Outreach emails will state that the coach has noticed they have not completed sleep diaries or worn the Fitbit in a few days and ask if they would like troubleshooting help or to return to the program. It will not include any coercive language or pressure. Email communication will be limited to pre-scripted content reminders and participant outreach.
7. Participants will be informed that they may discontinue the intervention at any time. In the event that an adverse event is experienced participants will be instructed to contact [name] or [name]. Phone numbers will be provided through which one of the investigators can be reached 7 days/week, 24 hours/day.
8. If during the protocol, the A1C is found to be  $>6.5\%$  but less than  $7\%$ , the participants will be kept in the study but informed of the test results at the end of the protocol. If A1C is  $>7\%$ , the will be discontinued from the study as this will require medical treatment from their primary care physician.

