sleep and basic counseling principles. They will establish **goals** with the participants based on the participants' values and beliefs, including sleep-related goals and usage goals (e.g., number of days wearing the sleep tracker). **Performance monitoring** will be completed through an online dashboard visible to the coach (Fitabase Inc.). The dashboard will contain data from sleep diaries and the wearable sleep tracker. The first coaching session will be a 20-min engagement session, which includes introductions, rationale for the program, roles of the coach, and the participants' goals for the program. Coach will provide feedback to the participant based on wearable sleep tracker data. For coaching sessions 2-8, the coach and participant will also have weekly brief (5-10 min) follow-up support calls to review progress, problem solve barriers to progress, and set goals for the following week. Between sessions, coach will be available to troubleshoot any problems. The use of coaching has been demonstrated to improve adherence to technology-based interventions. Drs. [name] and [name] have extensive experience in the use of coaching to improve adherence to technology-based interventions.

8.5 Hunger rating based on visual analog scale (0-100) will be given to the subjects to fill one day per week, in the morning before breakfast and before bedtime.

**9. Attention control: Health Education.** Use of a control group is to control for the coach contact in the intervention group. Participants assigned to the control group will be provided weekly health education emails (e.g., nutrition, stretching exercises; Appendix A). They will be instructed to maintain their sleep schedule but not monitored with diaries or coaching, a technique that produces little change in sleep timing. Participants will receive weekly brief telephone contact from the coach ( $\leq 5$  min) to answer questions. They will be asked to fill the visual analog scale for hunger one day per week (once in the morning before breakfast and once before bedtime). After the final follow-up, control participants will receive a Fitbit fitness tracker and PDF files of the 6 didactic lessons by mail.

All procedures in the protocol are research related. The research will take place at the College of Nursing, [name] or at the Clinical Research Center.

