### 13.3 Unanticipated Problems

#### Procedures for identifying, reviewing, and reporting adverse events and unanticipated problems to the IRB.

Throughout the study, [name] will monitor the participants for adverse events (AEs). [name] and study staff will review AEs individually in real time and in aggregate on a monthly basis and consult with co-investigators as needed. [name] will review serious adverse events (SAEs) in real time. [name] will ensure that all protocol deviations, AEs, and SAEs are reported to the UIC IRB according to applicable IRB requirements, and corrective actions will be taken as deemed necessary by the IRB. Events determined by the PI to be unanticipated problems that are SAEs involving risks to subjects or others will be reported by the PI to the UIC IRB per IRB policy or within 1 week. Unanticipated problems that are determined by the PI to be not serious will be reported per IRB policy or within 2 weeks.

All study staff will be informed by [name] about AEs. If any protocol changes are needed, a modification request will be submitted to the UIC IRB. Protocol changes will not be implemented prior to IRB approval unless necessary to eliminate apparent immediate hazards to the research subjects. In such a case, the IRB will be promptly informed of the change following implementation, according to IRB policy.

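### No visit or call is described as asking about adverse events, and call contact differs by arm, so event ascertainment may differ between the arms

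*Combined protocol and SAP*

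**What the plan says.** **How events come to light.** Section 7.0, Protections Against Risk, item 7: "In the event that an adverse event is experienced participants will be instructed to contact" one of two investigators, who can be reached by telephone at any hour. Item 2 of the same list, on distress from questionnaires, is also reactive: "study staff will be aware of the possibility and address any concerns that are voiced". Section 13.3 gives a named person the duty of monitoring participants for adverse events throughout the study, but does not say what is asked, on what form, or when. The baseline, week 7 and week 10 procedure lists in Section 6.0 and the Protocol Overview table contain no adverse-event item.

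**Contact by arm.** In the sleep-extension arm (Section 6.0, item 8.4), a 20-minute first session is followed by "weekly brief (5-10 min) follow-up support calls to review progress, problem solve barriers to progress" and set goals, and the coach can be reached for troubleshooting between sessions. In the control arm (item 9), "Participants will receive weekly brief telephone contact from the coach", of at most 5 minutes, so that questions can be answered.

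**Review.** Under Section 13.3, the monitor and staff "will review AEs individually in real time and in aggregate on a monthly basis". Of serious events it says that a named person "will review serious adverse events (SAEs) in real time". Unanticipated problems go to the IRB per its policy or within 1 week if serious and 2 weeks if not. Under the Data Safety Monitoring Plan in Section 11.0, the investigators "will meet with the SMC annually and provide a written and verbal progress report", and that report includes adverse events.

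**The concern.** Real-time and monthly review can only work on events that someone has already reported. If nobody asks, the count depends on which women volunteer what, and that plausibly depends on how much they talk to study staff and about what. Here those conversations differ by arm by design. The direction one would expect is more complete capture on sleep extension, which would make the intervention look less well tolerated than it is, or leave control-arm events unrecorded.

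What is at stake is the interpretability of any table of events by arm. The glucose outcomes are not affected. An event that was never asked about is hard to recover afterwards, so the matter is best settled before the calls and visits take place.

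**Working it through.** The protocol states no adverse-event rate and no adverse-event comparison, so there is no figure of its own to reproduce. The check sets the sections side by side, then does the arithmetic that the documents support.

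**Step 1. Is there scheduled elicitation?**

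| Place | What it provides |
|---|---|
| 7.0, Protections Against Risk, items 2 and 7 | Woman contacts an investigator, or voices a concern |
| 13.3 | Monitoring duty and review frequency; no question or time point |
| 6.0, baseline, week 7 and week 10 lists | Questionnaires, blood tests, actigraphy; no adverse-event item |
| Protocol Overview table | No adverse-event column |
| 6.0, items 8.4 and 9 (calls) | Neither call is described as asking about adverse events |

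No scheduled question is described in either arm.

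**Step 2. How different is scheduled call contact?** Inputs from Section 6.0: first sleep-extension session 20 min; later calls 5-10 min; control calls at most 5 min; weekly in both arms. Item 8.4 numbers the sessions up to 8, while the procedures describe 6 weeks, so both counts are shown.

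- Six calls, sleep extension: 20 + 5 × 5 = 45 min to 20 + 5 × 10 = 70 min. Control: at most 6 × 5 = 30 min. Ratio at least 45/30 = 1.5; with full-length control calls, up to 70/30 = 2.3.
- Eight calls, sleep extension: 20 + 7 × 5 = 55 min to 20 + 7 × 10 = 90 min. Control: at most 8 × 5 = 40 min. Ratio at least 55/40 = 1.4; with full-length control calls, up to 90/40 = 2.3.

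On either count, scheduled contact is at least about 1.4 times as long in the sleep-extension arm. Between-session troubleshooting comes on top. So do the outreach emails about missed diaries or Fitbit wear (Protections Against Risk, item 6). In practice those can reach only that arm: controls are not monitored with diaries and receive a Fitbit only after final follow-up.

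**Step 3. What would unequal capture do?** Recorded risk in an arm = true risk × share of events ascertained. Hence

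recorded risk ratio = true risk ratio × (share ascertained on sleep extension ÷ share ascertained on control).

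With equal shares the second factor is 1 and the true ratio is recovered. With unequal shares the recorded ratio is off by exactly that factor. The documents give neither share, and minutes of contact do not convert into one. A numerical bias would only restate whatever shares were assumed, so none is offered.

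**Step 4. Why denominators matter.** With 60 women randomized 2:1 (Sections 2.0 and 12.0), the arms are 60 × 2/3 = 40 and 60 × 1/3 = 20. Equal risk and equal capture would still give raw counts of 40:20 = 2:1.

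**Step 5. What the safety committee sees.** Its only stated access to events is the annual report; the reporting chain in Section 13.3 does not mention it. A woman's course after randomization runs to about week 11 (a week of actigraphy given at week 10), and 52/11 = 4.7 such courses fit in a year. A woman can therefore finish before the committee's next scheduled look, although investigators and the IRB would have been informed earlier under Section 13.3.

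**The case against.** The strongest reply is that detection does not rest on volunteering alone. Section 13.3 imposes an active duty to monitor. Both arms complete depression, anxiety and stress questionnaires at baseline, week 7 and week 10, have A1C and an OGTT at baseline and week 7, and give a participant evaluation with an interview. Most of the risks listed in Section 7.0 arise from, or are measured by, procedures common to both arms. Appendices A and B are not in the text available here, so it cannot be excluded that they include a relevant question. The study is a 60-woman behavioural pilot that the protocol regards as minimal risk. All of this stands, and it limits how much is likely to be missed. It does not supply a question about health problems in general, asked the same way in both arms. The guidance text left in Section 11.0 itself asks minimal-risk studies to describe how potential problems will be monitored.

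Three stronger readings are tempting and are not supported:

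- A reader might infer that the sleep-extension calls probe for adverse events and the control calls do not. The text concerns barriers to sleep goals. Calls are weekly in both arms, controls can raise matters on theirs, and neither call is described as asking about events. The difference is one of length and theme.
- A reader might infer that event counts are biased by a known amount. Unequal capture is plausible but not shown, its size cannot be derived, and Section 12.0 plans no comparison of events by arm. The exposure is to any such comparison made later.
- A reader might infer from the annual meeting that serious events go unseen for a year. Real-time review of serious events, monthly aggregate review and IRB reporting within 1 to 2 weeks rule that out. The committee is one layer of oversight among several, and moving its first review would be a matter of preference.

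**Conclusion.** The point holds in limited form. The protocol describes no systematic elicitation of adverse events. Scheduled call contact is at least 1.4 to 1.5 times as long on sleep extension as on control, and its content is more problem-oriented. Ascertainment may therefore differ by arm, and any comparison of events by arm may be biased, most plausibly towards more recorded events on sleep extension. That direction rests on the assumption that longer, problem-solving contact brings out more spontaneous reports. The size cannot be estimated from the documents.

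The committee's access to events is limited to the annual report, a minor gap given the other review that exists. This is an inexpensive improvement to make, not a flaw that undermines the trial's main analysis.

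**What to change.** 1. Add one identical scripted open question, asking about any new health problem since the last contact, to every existing weekly call in both arms (Section 6.0, items 8.4 and 9) and to the week 6-7 and week 10 visit lists. Add a matching column to the Protocol Overview table, and refer to the question in Section 13.3 as the means of monitoring.
2. State in Section 12.0 that events will be reported by arm, descriptively, with the number of women randomized to that arm as the denominator.
3. Reconcile the number of coaching sessions in item 8.4 with the 6-week procedures, so that the number of contacts at which the question is asked is fixed for both arms.
4. Optionally, copy the safety monitoring committee on the serious-event and unanticipated-problem reports that Section 13.3 already sends to the IRB.

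The cost is small: one question in calls and visits that already take place, one table column, and, if item 4 is adopted, one more addressee. The downside is a somewhat higher count of minor events. The question equalises the asking but not the length of the calls, so some difference in what is volunteered may remain.
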